8.9.2.2 Suspected Adverse Reaction

A suspected adverse reaction (SAR) is defined as any AE for which there is reasonable possibility that the drug caused the AE (21 CFR 312.32 (a)).

8.9.2.3 Unexpected Adverse Event

An AE or SAR is considered unexpected if it is not consistent with the risk information described in the labeling for the study products.

8.9.2.4 Serious Adverse Event

An SAE is defined as any AE or SAR that, in the view of the investigator or sponsor, results in any of the following outcomes (21 CFR 312.32 (a)):

- Death
- Life-threatening AE (Note: the term “life-threatening” as used here refers to an event that in the view of the investigator or sponsor places the subject at immediate risk of death at the time of the event; it does not include an AE or SAE that, had it occurred in a more severe form, might have caused death [21 CFR 312.32(a)])
- Inpatient hospitalization or prolongation of existing hospitalization
- Persistent or significant incapacity or substantial disruption of the ability to conduct normal life functions
- Congenital anomaly/birth defect
- Any “other” important medical event. Important medical events that may not result in death, be life-threatening, or require hospitalization may be considered serious when, based upon appropriate medical judgment, they may jeopardize the subject and may require medical or surgical intervention to prevent one of the outcomes listed in this definition. Examples of such medical events include allergic bronchospasm requiring intensive treatment in an emergency room or at home, blood dyscrasias or convulsions that do not result in inpatient hospitalization, or the development of drug dependency or drug abuse.

8.9.2.5 Planned Hospitalization

A hospitalization planned by the subject prior to signing the ICF is considered a therapeutic intervention and not the result of a new SAE and should be recorded as medical history. If the planned hospitalization or procedure occurs as planned, the record in the subject’s medical history is considered complete. However, if the event/condition worsens during the study, it must be reported as an AE.

8.9.2.6 Pregnancy

Pregnancies occurring after the administration of study product require immediate reporting. They must be reported within 24 hours after the investigator has become aware of the pregnancy. A pregnancy report will be completed and sent by fax to Symbio within 24 hours of becoming aware of the pregnancy. The investigator will collect follow-up information regarding the outcome of the pregnancy and any postnatal sequelae in the infant that must also be reported to the sponsor or designee. Upon awareness of the outcome of the pregnancy, the PI or designee must forward a follow-up Pregnancy Report with any relevant information to Symbio.

If the outcome of the pregnancy meets the criteria for immediate classification of an SAE (e.g., spontaneous abortion, stillbirth, neonatal death, or congenital anomaly), the investigator will report the event by faxing a completed SAE report form to Symbio within 24 hours of being notified of the pregnancy report.

The subject should immediately be withdrawn from the study.

8.9.2.7 *Monitoring*

8.9.3 *Monitoring Adverse Events and Laboratory Evaluations*

Each subject will be monitored for the occurrence of AEs, including SAEs, immediately after treatment initiation. Each subject will be followed for safety monitoring until discharged from the study. Follow-up procedures related to pregnancy or AEs or SAEs may continue beyond the end of the study.

Subjects will be questioned and/or examined by the investigator or a qualified designee for occurrence of AEs throughout the study. The presence or absence of specific AEs should not be elicited from subjects. In addition, subjects will be instructed to record AEs on the subject diary card during the 2 weeks after treatment. Subjects having AEs will be monitored with relevant clinical assessments and laboratory tests, as determined by the investigator.

AEs, actions taken as a result of AEs, and follow-up results must be recorded on the CRF, as well as in the subject's source documentation.

For all AEs that require the subject to be withdrawn from the study and SAEs, relevant clinical assessments and laboratory tests will be repeated as clinically appropriate until final resolution or stabilization of the event(s).

8.9.4 *Assessment of Adverse Events*

8.9.4.1 *Assessment of Severity*

Severity of AEs will be graded according to the following definitions:

Mild: AE that was easily tolerated

Moderate: AE sufficiently discomforting to interfere with daily activity

Severe: AE that prevented normal daily activities

8.9.4.2 *Assessment of Causality*

A medically-qualified investigator must assess the relationship of any AE (including SAEs) to the use of the study product, as unlikely related, possibly related, or probably related, based on available information, using the following guidelines:

Unlikely related: no temporal association, or the cause of the event has been identified, or the drug, biological, or device cannot be implicated based on available information

Possibly related: temporal association but other etiologies are likely to be the cause; however, involvement of the drug, biological, or device cannot be excluded based on available information

Probably related: temporal association, other etiologies are possible, but unlikely based on available information

8.9.4.3 *Reference Safety Information for Assessing Expectedness of Adverse Events*

The reference safety information for assessing the expectedness of an AE for the study product in this study is the [Restylane package insert \(2011\)](#). As reported by the subjects following injection with Restylane in 3 clinical studies, the most frequent injection-site responses were

bruising (47% to 78% of subjects by study), redness (58% to 85%), swelling (83% to 89%), pain (57% to 76%), tenderness (78% to 87%), and itching (30% to 47%).

8.9.5 Reporting Safety Observations

Any SAE, whether deemed product-related or not, must be reported to Symbio by telephone or fax as soon as possible after the investigator or coordinator has become aware of its occurrence. The investigator/coordinator must complete a Serious Adverse Event (SAE) Form and fax it to Symbio along with the subject's Adverse Events Log and Concomitant Medications Log within 24 hours of notification of the event. Symbio will notify the sponsor immediately upon notification of the event from a study site to allow for reporting to the United States Food and Drug Administration (FDA) in a timely fashion. The sponsor will notify the FDA of drug-related SAEs.

Symbio contact details:

[name] Medical Monitor Direct: [name] or [name] [contact] [contact]	[name] Director, Clinical Operations Direct: [contact] [name] [contact]	Symbio, LLC [name] [contact] [contact]
---	---	--

Sponsor contact details:

[name] Managing Director Prollenium Medical Technologies Inc. [name] CANADA [contact] [contact]

The investigator must be prepared to supply the medical monitor with the following information:

1. Investigator name and site number
2. Protocol number
3. Subject ID (screening/randomization) number
4. Subject initials and date of birth
5. Subject demographics

6. Clinical event
 - a. description
 - b. date of onset
 - c. severity
 - d. treatment (including hospitalization)
 - e. relationship to study product
 - f. action taken regarding study product
 - g. if the AE was fatal or life-threatening:
 - i. cause of death (whether or not the death was related to study product)
 - ii. autopsy findings (if available)

The Sponsor must submit a written summary of the clinical course of any life-threatening SAE and related subject information to the FDA within 7 days. Serious and unexpected AEs that are not life-threatening must be reported to the FDA within 15 calendar days. Any serious and unexpected AE (including all deaths) must also be reported to the IRB/IEC by the investigator according to IRB reporting requirements and documentation of this report sent to Symbio.

The investigator must provide a follow-up written report within 5 calendar days of reporting the event to the medical monitor. The written report must contain a full description of the event and any sequelae. Subjects who have had an SAE must be followed clinically until all parameters (including laboratory) have either returned to normal or are stabilized.

8.9.6 Withdrawal, Treatment Interruption, and Unblinding of Blinded Treatment Due to Safety Observations

8.9.6.1 Withdrawal

See [Section 8.3.3](#) for the criteria for withdrawing a subject. If a subject is withdrawn from the study, the activities specified for Visit 6/Week 24 on the Study Flow Chart ([Section 3.2](#)) should be completed if possible.

8.9.6.2 Unblinding Treatment for a Subject During the Study

Unblinding by the investigator should occur only in the event of an AE or SAE for which it is necessary to know the study treatment to determine an appropriate course of therapy for the subject. In the event of an emergency that requires breaking of the study blind, randomization code envelopes will be maintained by each investigator that can be opened to reveal the study product.

Envelopes that have been opened at the study site must be returned to the sponsor accompanied by a written explanation of the reason why the blind was broken.

If unblinding occurs, the subject must be withdrawn from the study.

8.10 Criteria for Early Termination of the Study

The trial may be terminated because of safety concerns. Where termination is deemed appropriate, there will be timely communication with FDA in accordance with the regulation (21 CFR 812.150 (devices)). The sponsor, Prollenium Medical Technologies, will initiate discussion as soon as possible about the appropriate course of action for the trial in question and for the investigational product. There will be immediate follow up by the company to investigate any potential safety concern.

The clinical study may be stopped if the extent (incidence and/or severity) of emerging effects/clinical endpoints is such that the risk/benefit ratio to the study population as a whole is unacceptable. In the event of an unanticipated serious adverse event or death, the sponsor, Prollenium Medical, will submit to the agency, and to the reviewing IRB, a report as soon as possible, but in no event later than 10 working days after the investigator / sponsor first learns of the effect. Thereafter the sponsor shall submit such additional reports concerning the effect as FDA requests.

The following conditions are considered as cause for termination of the study:

Any death related to the study treatment

Unanticipated treatment emergent related AEs reported as severe in the opinion of the Investigator in > 7 of the subjects

Unanticipated treatment emergent related AEs reported as moderate in the opinion of the Investigator in > 43 of the subjects

Unanticipated treatment emergent related AEs reported as mild in the opinion of the Investigator and unresolved at 14 days in > 98 of the subjects

Duration of AEs lasting more than 4 weeks

Increased incidence of Physician diagnosed unexpected AEs

Increased occurrence of extreme swelling of the face, hypersensitivity reactions/anaphylaxis

Anticipated Adverse Effects: The following conditions are expected following injection, the data in the table below is the adverse effect incidence in the Restylane studies (see Restylane P020023b [Table 1](#), [Table 2](#)). They will not be cause for early stopping of the study, unless the AE rate is deemed too high during the weekly reviews, or they are severe, or unresolved:

Condition	Anticipated rate of occurrence at 24 hours /14 days
Redness / Erythema	13.8 % / 8.7 %
Swelling and / or edema	11.6 % / 2.9 %
Ecchymosis and / or bruising	5.1 % / 2.2 %
Tenderness	15.2 % / 1.4 %

Pain	21.0 % / 0.0 %
Itching	8.0 % / 0.0 %
Other	5.1 % / 0.7 %

Unanticipated adverse events related to the injection will be evaluated as they occur by the sponsor and physician (* these may include injection site adverse events not listed above, such as Hyperpigmentation, Pruritus, Papule, Burning, Hypopigmentation, Injection Site Scab). These events will be evaluated based on their severity and duration, and if deemed necessary, the study will be stopped.

Any serious adverse event, and / or systemic response, or condition, that requires hospitalization following injection, in particular those deemed related to the injection, will be evaluated based on their severity and duration, and if deemed necessary, the study will be stopped.

All reported events will be reviewed on a weekly basis during the clinical study team meeting.

In addition, further recruitment in the study or at (a) particular site(s) may be stopped due to insufficient compliance with the protocol, GCP, and/or other applicable regulatory requirements, procedure-related problems, or the number of discontinuations for administrative reasons is too high.

9 STATISTICAL METHODS

Prior to the database lock, a detailed, finalized Statistical Analysis Plan will be completed and placed on file. The Statistical Analysis Plan will contain a more comprehensive explanation than that provided here of the methodology used in the statistical analyses, as well as the rules and data handling conventions used to perform the analyses and the procedure used to account for missing data.

9.1 Analysis Populations

Three populations are defined for the analyses.

- Intent-to-treat (ITT) (safety population): All randomized subjects who received study product.
- Modified intent-to-treat (mITT): All randomized subjects who met the inclusion/exclusion criteria, were randomized, received both study products, and returned for at least 1 post-injection assessment of WSRS score from both sides of the face.
- Per-protocol (PP): All randomized subjects who met all inclusion/exclusion criteria; received both study products; completed Visit 6/Week 24 within the specified window, had data on WSRS score from both sides of the face, and had no significant protocol violations that would affect the treatment evaluation.

Efficacy analyses will be performed on the mITT and PP populations. Safety analyses will be performed on the ITT population.

9.2 General Considerations

Two-sided hypothesis testing will be conducted for all tests. Resulting p-values less than 0.05 will be considered statistically significant unless noted otherwise. No adjustments of p-values for multiple comparisons will be made. SAS software (version 9.1.3) will be used for all data analyses and tabulations.

Missing efficacy data will be imputed via the last observation carried forward (LOCF) method in the mITT analysis. For the PP population, efficacy analysis will be performed using all the available data without imputation for the missing values.

For demographic and baseline characteristics and the safety profile, each variable will be analyzed using the existing data. Subjects with missing data will be excluded only from the analyses for which data are not available.

9.3 Comparability of Subjects at Baseline (or Demographics, Medical History, Baseline Characteristics, and Concomitant Medications)

Baseline and demographic characteristic variables (including date of birth, sex, race, ethnicity, and Fitzpatrick skin type) will be tabulated using descriptive statistics. For each continuous variable, the summary will include the mean, standard deviation, median, minimum and maximum. For each categorical variable, the summary will include frequencies and percentages.

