A subject may be withdrawn from the study for any of the following reasons:

- Lost to follow-up
- Investigator discretion

Withdrawal is permanent; after a subject has been withdrawn, he/she will not be allowed to enroll again.

If a subject is withdrawn from the study for any reason, the End of Study or Early Termination procedures (Visit 6/Week 24 for subjects who are not retreated at Week 24 or Visit 8/Week 52 for subjects who are retreated at Week 24) should be completed and any outstanding data and study product should be collected. Data, including the date and primary reason for withdrawal, must be documented on the End of Study case report form (CRF) and source document.

If a subject withdraws from the study at any time due to an AE, the reason for withdrawal, the nature of the AE, and its clinical course must be fully documented. The investigator must strive to follow the subject until the AE has resolved, become clinically insignificant, is stabilized, or the subject is lost to follow-up. For any SAE, follow procedures provided in [Section 8.9.5](#)

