8.5 Study Schedule

The visit-by-visit schedule of study activities is provided in the Study Flow Chart in [Section 3.2](#). The timing of each visit is relative to Day 1, which is defined as the day the subject is randomized and treated.

All visits should be performed within the windows specified on the Study Flow Chart. Every attempt should be made to have each subject attend each visit as scheduled. If a subject is unable to attend a visit within the specified window the visit should be scheduled as closely as possible to the applicable window.

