8.6.7 Wrinkle Severity Rating Scale (WSRS)

The WSRS Score is a 5-point scale with the following categories:

1. Absent - No visible fold; continuous skin line.
2. Mild - Shallow but visible fold with a slight indentation; minor facial feature; implant is expected to produce a slight improvement in appearance.
3. Moderate - Moderately deep folds; clear facial feature visible at normal appearance but not when stretched; excellent correction is expected from injectable implant.
4. Severe - Very long and deep folds; prominent facial feature; less than 2 mm visible when stretched; significant improvement is expected from injectable implant.
5. Extreme - Extremely deep and long folds, detrimental to facial appearance; 2 to 4 mm visible V-shaped fold when stretched; unlikely to have satisfactory correction with injectable implant alone.

The WSRS score will be assessed for each NLF at every study visit through Visit 6/Week 24 (Visit 1/Day 1, Visit 2/Week 1, Visit 3/Week 2, Visit 4/Week 4, Visit 5/Week 12, and Visit 6/Week 24 [End of Study/Early Termination for subjects who are not retreated]) by a blinded evaluator (blinded to the treatment assignment of each NLF). For subjects who are retreated, this will also be assessed at Visit 7/Week 28 and Visit 8/Week 52 (End of Study/Early Termination) but the evaluator does not need to be blinded for those assessments.

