9.4 Efficacy Evaluations

The primary efficacy variable is change from Baseline to Week 6/Week 24 in WSRS score. Summary statistics (mean, SD, minimum, median, maximum) and 95% confidence interval (CI) will be presented for the changes scores for each treatment and for the difference in change scores between the two treatment groups (Comparator minus Test product, i.e., Restylane minus Revanesse). The 95% CI for difference between treatments will be constructed assuming a normal distribution of the change scores. If the upper bound of this 95% CI is less than the pre-specified non-inferiority (NI) limit (i.e. 0.50), the Test product will be claimed to be non-inferior to the Comparator product.

Secondary efficacy endpoints include the responder rate, i.e., the percentage of subjects with treatment success (defined as at least a 1-grade improvement in WSRS from baseline to Week 24), pGAI score at Visit 6/Week 24, and iGAI score at Visit 6/Week 24. For these secondary variables, the null hypothesis to be tested is that there is no difference between the two products. The variables responder rate, pGAI and iGAI scores at Visit 6/Week 24 will be tabulated with frequencies and percentage and analyzed using the Wilcoxon matched-pairs signed rank test.

Other efficacy variables include change in WSRS score, pGAI, and iGAI at Visit 2/Week 1, Visit 3/Week 2, Visit 4/Week 4, and Visit 5/Week 12. Treatment difference with respect to these variables will be examined using descriptive summaries.

All efficacy analyses will be performed for both the PP and mITT populations. For the primary endpoint, the results from PP are considered definitive and those from mITT supportive.

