15 APPENDICES

15.1 Package Insert for Revanesse Ultra

COMPOSITION

Cross-linked hyaluronic acid (High Viscosity) 25mg/ml
In phosphate buffered saline
[Cross linked with Butandiol-diglycidylether (BDDE)]

DESCRIPTION

Revanesse® Ultra is a colorless, odorless, transparent and aqueous gel of synthetic origin. The gel is stored in a pre-filled disposable syringe. Each box contains two 1ml syringes of Revanesse® Ultra along with two sterilized needles.

APPLICATION RANGE / INDICATIONS

Revanesse® Ultra is a cross linked hyaluronic acid gel that is indicated for the filling of medium size and deep wrinkles of the face by injection into the middle part of the dermis layer. Implantation life is dependent on depth and location and averages 6-12 months.

ANTICIPATED SIDE EFFECTS

Physicians must inform patients that with every injection of Revanesse® Ultra there are potential adverse reactions that may be delayed or occur immediately after the injection. These include but are not limited to:

- Injection-related reactions might occur, such as transient erythema, swelling, pain, itching, discoloration or tenderness at the injection site. These reactions may last for one week.
- Nodules or induration are also possible at the injection site.
- Poor product performance due to improper injection technique.
- Glabellar necrosis, abscess formation, granulomas and hypersensitivity have all been reported with injections of hyaluronic acid products. It is important for physicians to take these reactions into account on a case by case basis.

Reactions thought to be of hypersensitivity in nature have been reported in less than one in every 1500 treatments. These have consisted of prolonged erythema, swelling and induration at the implant site.

These reactions have started either shortly after injection or after a delay of 2 - 4 weeks and have been described as mild or moderate, with an average duration of 2 weeks. Typically, this reaction is self-limiting and resolves spontaneously with time. However, it is imperative that patients with hypersensitivity type reactions contact their physician immediately for assessment. Patients with multiple allergic reactions should be excluded from the treatment.

CONTRAINDICATIONS

- Do not inject Revanesse® Ultra into eye contours (into the eye circle or eyelids).
- Pregnant women, or women during lactation should not be treated with Revanesse® Ultra.

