Endpoints Demographics: The study enrolled a population of predominately healthy, female, Caucasian non-smokers with history of prior facial aesthetic procedures and minimal sun exposure. There were few men or other racial/ethnic groups; few smokers or patients with extensive sun exposure. 
 
 Gender	* Tobacco use			
 
 Male: 9 (6.0%)	Non-smokers: 118 (86.1%)			
 
 Female: 128 (93.4%)	Smokers: 19 (13.9%)			
 
 
 
 • Ethnicity	* Sun Exposure			
 
 Caucasian: 122 (89.0%)	None: 83 (60.6%)			
 
 Black: 2 (1.5%)	Natural Sun: 52 (38.0%)			
 
 Asian: 2 (1.5%)	Artificial: 2 (1.5%)			
 
 Hispanic: 11 (8.0%)				
 
 Effectiveness Primary: Based on the per patient evaluation, the WSRS scores at 6 months by the evaluating investigator demonstrated that WSRS for	Gender	* Tobacco use			Male: 9 (6.0%)	Non-smokers: 118 (86.1%)			Female: 128 (93.4%)	Smokers: 19 (13.9%)			• Ethnicity	* Sun Exposure			Caucasian: 122 (89.0%)	None: 83 (60.6%)			Black: 2 (1.5%)	Natural Sun: 52 (38.0%)			Asian: 2 (1.5%)	Artificial: 2 (1.5%)			Hispanic: 11 (8.0%)				Endpoints Demographics: The study enrolled 283 (i.e., 142 Restylane and 141 Perlane) patients with moderate to severe NLF wrinkles. The patients were predominantly healthy ethnically diverse females. Bilateral NLFs and oral commissures were corrected with 2.1 mL to 5.2 mL of Restylane. The greatest amount used in any patient was 8.8 mL. Gender – Female: 266 (94%); Male: 17 (6%) Ethnicity – White: 226 (80%); Hispanic or Latino: 31 (11%); African American: 23 (8%); Asian: 3 (1%) Efficacy: The results of the blinded evaluator assessment of NLF wrinkle severity for Restylane and control (Perlane) are presented in Table 15. In the primary effectiveness assessment at 12 weeks, 77% of the Restylane and 87% of the control patients had maintained at least a 1-point improvement over baseline.	Outcomes Table 14. Blinded Evaluator Mean Wrinkle Severity Scores 
  
 	N	Restylane	Control	Absolute Difference	
   
 Pre-treatment	138	3.29	3.31	0.02	
 
 Baseline	138	1.80	1.79	0.01	
 
 6 months	134	2.36	2.94	0.58	
  
		N	Restylane	Control	Absolute Difference	Pre-treatment	138	3.29	3.31	0.02	Baseline	138	1.80	1.79	0.01	6 months	134	2.36	2.94	0.58	Table 15. Blinded Evaluator Wrinkle Severity Response Scores 
  
 Time point	No. of Restylane Patients	No. of Restylane Pts. maintaining ≥ 1 Unit Improvement of NLF on WSRS	No. of Perlane Patients	No. of Perlane Pts. maintaining ≥ 1 Unit Improvement of NLF on WSRS	
   
 6 weeks	136	113 (83%)^a	136	121 (89%)	
 
 12 weeks	140	108 (77%)^a	141	122 (87%)	
 
 24 weeks	140	103 (74%)^a	138	87 (63%)	
  
 
^aAll p-values <0.0001 based on t-test compared to baseline condition
	Time point	No. of Restylane Patients	No. of Restylane Pts. maintaining ≥ 1 Unit Improvement of NLF on WSRS	No. of Perlane Patients	No. of Perlane Pts. maintaining ≥ 1 Unit Improvement of NLF on WSRS	6 weeks	136	113 (83%) ^a	136	121 (89%)	12 weeks	140	108 (77%) ^a	141	122 (87%)	24 weeks	140	103 (74%) ^a	138	87 (63%)

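### LOCF in the supportive mITT analysis lets an early wrinkle rating stand for Week 24; a repeated-measures model is a cheap improvement

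*Protocol*

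**What the plan says.** Section 9.2 fixes the method: "Missing efficacy data will be imputed via the last observation carried forward (LOCF) method in the mITT analysis". The same section leaves the PP analysis unimputed. The opening of section 9 says the SAP will expand on missing data, but the method for mITT is already chosen here.

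Section 9.1 admits to mITT eligible subjects who received both products and "returned for at least 1 post-injection assessment of WSRS score from both sides of the face". A single Week 1 rating satisfies that.

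Section 9.4 runs all efficacy analyses in both populations and ranks them: "For the primary endpoint, the results from PP are considered definitive and those from mITT supportive".

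Two rules affect which values are carried. Section 8.3.3 says "If a subject is withdrawn from the study for any reason, the End of Study or Early Termination procedures" should be completed, so a withdrawn subject may have a Visit 6-type rating taken well before Week 24. Section 8.5 says that, for a subject who cannot attend in window, "the visit should be scheduled as closely as possible to the applicable window"; such a subject should still have an observed rating.

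Section 8.6.7 provides the data for an alternative: "The WSRS score will be assessed for each NLF at every study visit through Visit 6/Week 24".

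On durability, the Revanesse Ultra insert (15.1) says "Implantation life is dependent on depth and location and averages 6-12 months". The Restylane insert (15.2) gives responder rates over time in its Table 16 and in "Table 15. Blinded Evaluator Wrinkle Severity Response Scores".

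**The concern.** LOCF assumes that nothing changes after the last rating. For a resorbable filler assessed at six months that is doubtful, and the comparator's own insert contradicts it. Two things could be affected.

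- **The mITT paired contrast.** Its job is to check whether PP's exclusions matter. If the two products fade at different speeds, a carried value reports the early difference in place of the Week 24 difference. Should the test product fade faster, mITT would look closer to equivalence than Week 24 data would, and its agreement with PP would reassure too much. Should the comparator fade faster, the bias runs against the test product.
- **The per-fold mITT summaries.** Change in WSRS, responder rate, pGAI and iGAI on a given fold can be flattered even when both products fade alike, because there is no pairing to cancel the fading.

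The affected subjects are only the eligible ones with no Week 24 rating at all.

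**Working it through.** **1. Reproduce the plan's figure.** Section 9.6 gives margin 0.50, SD of the paired difference 1.30 and true difference 0; the decision uses the upper limit of a two-sided 95% CI. Noncentrality at n = 63 is 0.50 / (1.30/√63) = 3.05. The noncentral t (62 df) gives power 85.2%, and 63 is the smallest n reaching 85%. The stated 63 reproduces.

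**2. Direction.** In the previous study (9.6) improvement was 3.22 − 2.34 = 0.88 for Revanesse and 3.20 − 2.41 = 0.79 for Restylane. Comparator minus test is −0.09, close to the plan's −0.095. So change is counted as improvement, and a positive difference means the test product does worse.

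**3. How many values would be carried.** The protocol states no expected missingness. In the insert, subjects rated at 6 months or 24 weeks were 134/138, 140/142, 138/141 and 147/150, so 2.9%, 1.4%, 2.1% and 2.0% were missing. Applied to 163 subjects, 1.4% to 2.9% is about 2 to 5. A figure of 10% (about 16) is an assumption.

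**4. Does the effect fade before Week 24?** Restylane responders (at least one grade better):

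| Insert study | 6 weeks | 12 weeks | 24 weeks |
|---|---|---|---|
| Table 16, split face | 142/148 (96%) | 139/149 (93%) | 108/147 (73%) |
| Table 15, parallel groups | 113/136 (83%) | 108/140 (77%) | 103/140 (74%) |

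For the comparator, yes, though by very different amounts from Week 12 on. Both studies count weeks from optimal correction, while this trial counts from Day 1 (8.5). For the test product, section 9.6 gives only baseline and Month 6, and an average life of 6-12 months does not describe the course before Week 24.

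**5. Paired contrast, mITT alone.** With fraction f carried, early difference e and true Week 24 difference 0.50:

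expected difference = f·e + (1 − f)·0.50

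The chance that the upper limit falls below 0.50 comes from the noncentral t with n = 163, 162 df and standard error 1.30/√163 = 0.102.

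| f | e = 0: expected difference | e = 0: clears | e = 0.25: clears | e = 0.50: clears |
|---|---|---|---|---|
| 0 | 0.500 | 2.5% | 2.5% | 2.5% |
| 1.4% | 0.493 | 2.9% | 2.7% | 2.5% |
| 2.9% | 0.4855 | 3.5% | 2.9% | 2.5% |
| 10% (assumed) | 0.450 | 7.1% | 4.3% | 2.5% |

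The column e = 0 is the worst case considered: products equal early and a full 0.50 apart at Week 24. The column e = 0.50, where the difference does not change over time, shows no effect.

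**6. Per-fold responder rate, carried Week 12 rating.** Inflation = f × (12-week rate − 24-week rate).

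- Table 16: 139/149 − 108/147 = 19.8 points, giving 0.28, 0.57 and 1.98 points at f = 1.4%, 2.9% and 10%.
- Table 15: 108/140 − 103/140 = 3.6 points, giving 0.05, 0.10 and 0.36 points.

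**7. Would a repeated-measures model do better?** A simulation of 4,000 runs assumed differences of 0 at Weeks 1-4, 0.25 at Week 12 and 0.50 at Week 24, correlation 0.5 between visits, n = 163 and dropout completely at random. At 5% and 10% missing, LOCF gave mean estimates of 0.480 and 0.457 and false clearance of 3.9% and 6.0%. The model stayed at 0.50, with false clearance of 2.2% and 2.5%. Its standard error at 10% missing was 0.1046 against 0.1021, about 2% larger.

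**8. mITT as a check on PP.** The same worst case was simulated with one early rating and an assumed correlation of 0.5. Among trials where PP wrongly clears, mITT disagrees in about 6% with LOCF, 8% with the model and 16-17% with complete Week 24 data at 5 of 163 missing. At 16 of 163 the figures are about 3%, 16-17% and 30%. The model recovers little at 5 missing and more at 16; it does not reach the complete-data figure.

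**The case against.** The strongest reply is that no decision depends on this. PP is definitive and unimputed, equal fading cancels in a split-face contrast, and no document shows the two products fading unequally. All of that stands.

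A reader might infer that LOCF inflates the error rate of the non-inferiority claim. It does not, because that claim rests on PP. A reader might also infer that LOCF favours the test product. The documents do not establish that: they give no time course for the test product. For another pair of hyaluronic acid fillers (Restylane and Perlane), the insert shows near-identical courses in the split-face study (within about 2 points at each visit) and diverging ones in parallel groups (83/77/74% against 89/87/63%).

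Nor is a carried score always flattering. At Visit 2 the WSRS is listed before the touch-up evaluation (8.7.2), and an iGAI of 3 or 4 leads to a touch-up (8.6.11). A carried Week 1 rating may therefore precede further treatment and understate later correction.

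The disagreement figures in step 8 come from missingness completely at random, where PP is unbiased. They describe how closely mITT follows PP, not how well it detects selection in PP.

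What survives is that the method is fixed in current text, its assumption conflicts with the comparator data in the protocol's own appendix, and a better method can use ratings already scheduled.

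**Conclusion.** The point holds as a cheap improvement to a supportive analysis. It is not an error in the primary test, and the sample size and decision rule are unaffected.

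For the paired contrast it matters only if the products fade unequally. In the worst case considered, false clearance by mITT alone rises from 2.5% to 2.9-3.5% at the insert's missingness and to 7.1% at an assumed 10%. For per-fold responder rates, a carried Week 12 rating adds about 0.05 to 0.6 points at 1.4-2.9% missing and 0.4 to 2.0 points at 10%, depending on which insert study is used; a carried Week 1 rating may err the other way.

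These figures assume SD 1.30, all 163 subjects in mITT and missingness unrelated to outcome. The early differences, the 10% rate and the between-visit correlation are assumptions, not document figures.

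**What to change.** In section 9.2:

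- Make the mITT primary-endpoint analysis a repeated-measures model of WSRS change by fold and visit (Weeks 1, 2, 4, 12 and 24), with an unstructured or otherwise suitable within-subject covariance. Modelling by fold gives the per-fold Week 24 means as well as the paired Week 24 contrast; a model of the difference alone would leave the per-fold means on LOCF.
- Place Early Termination ratings at their actual time, and count them as Week 24 only if they fall inside the Visit 6 window of ±7 days.
- Keep LOCF as a sensitivity analysis.
- For mITT responder rate, pGAI and iGAI, show results on observed Week 24 data beside LOCF.

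The cost is some programming and a slightly wider mITT interval (about 2% in the simulation at 10% missing). No visit, procedure or subject is added, because each fold is already rated at all these weeks. The change should be made before database lock.
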